### Project summary

Cerebral Palsy (CP) is the most common motor disability in children born preterm. CP can cause profound disability, lifelong need for extensive care and result in significant economic burden. Ideally interventions should be initiated while at-risk infants are still admitted in the neonatal intensive care unit (NICU), at a stage of rapid brain development where intervention may have an impact on synaptic pruning and brain rewiring. Previous studies indicate that intervention focusing on environmental enrichment and emotional connection between mother and infant can positively impact the neurodevelopmental outcomes of infants born preterm. However, whether this type of interventions can improve the motor outcomes of infants at risk for CP remains unknown. To address this gap in knowledge, we have developed a NICU-based multimodal rehabilitation program (NeoRehab) to support neuromuscular development in preterm infants, This multimodal program, is composed of 6 evidencebased interventions (vocal soothing, scent exchange, comforting touch, kangaroo care, infant massage and physical therapy (PT)) administered in a gestational age (GA) appropriate fashion by a parent. We hypothesize that the NeoRehab program will positively impact short-term motor outcomes in preterm infants at risk for CP. At risk infants (≤32 week's gestation and/or ≤1500 grams birthweight) will be eligible for a pilot randomized controlled trial (RCT) comparing the effects of the NeoRehab program versus usual care on short term motor outcomes (general movements, cranial nerves, posture, movements, tone, and reflexes). The primary outcome is to determine the acceptability, feasibility and fidelity of the program by performing direct observation, weekly interviews and activity log reviews. Secondary short-term developmental outcomes will be measured using the Hammersmith Infant Neurological Examination (HINE) instruments, the general movement assessment (GMA), and the Test of Infant Motor Performance (TIMP) at 3 months postmentrual age (PMA). This study addresses one of the priorities of the National Center for Medical Rehabilitation Research to explore "multimodal rehabilitation approaches that promote plasticity and sensorimotor function". Results from this study will provide the preliminary evidence necessary to design and implement a large, multi-center RCT to test the efficacy of NICU-based rehabilitation programs to improve the motor outcomes of infants born preterm.

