# Study goals and objectives

The goal of this project is to investigate the acceptability, feasibility and fidelity of an innovative NICU rehabilitation program that will include six multimodal, GA appropriate, parent-administered interventions (vocal soothing, scent exchange, comforting touch, kangaroo care, infant massage and physical therapy). We will also determine the effects of this program on short-term motor outcomes using the HINE, the GMA and the TIMP instruments in premature infants (≤32 week's gestation and/or ≤1500 grams birthweight).

AIM 1: Enroll 60 preterm infants (<32 weeks' gestation and/or ≤1500 grams) into a pilot RCT to evaluate the acceptability, feasibility (practicality) and fidelity (adherence, exposure and engagement) of a multimodal GA appropriate rehabilitation program during NICU hospitalization compared to standard of care. We will evaluate:

- Acceptability using recruitment, refusal, retention, and follow-up rates as well as weekly interviews with parental participants
- Feasibility (practicality) using direct observations and weekly interviews with parental participants
- Fidelity (adherence, exposure and engagement) using visitation data, activity logs, direct observations, and weekly interviews.

AIM 2: Examine the effect of a multimodal NICU-based rehabilitation program on short-term motor outcomes (general movements, cranial nerves, posture, movements, tone, and reflexes) of premature infants at risk for CP at discharge from the NICU and at 3 months PMA. We hypothesize that this type of GA appropriate multimodal NICU-based rehabilitation program will positively impact short-term motor outcomes by normalizing general movements and improving TIMP and HINE scores.

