#### Inclusion and exclusion criteria:

Infants will be eligible for this study if they meet the following criteria:

- GA at birth: ≤32 weeks gestation and/or birthweight ≤1500 grams
- Infants 7 days or older
- Parental ability to perform the interventions or identified designated surrogate (e.g. grandparent)
- Abnormal writhing GMs defined by the presence of a poor repertoire pattern on 2 consecutive weeks or the presence of a cramped-synchronized pattern on any assessment (see **Figure 1**)

Infants will be excluded from the study if they are clinically unstable (requiring high frequency mechanical ventilation, vasopressor support, need for continuous intravenous pain or sedation medication), if their parents do not speak English or if parental participation is hindered (e.g. incarceration or work/personal related issues).

Figure 1: Intervention algorithm

Intervention (n=30): Parents will be provided oral as well as written (Flip book) and illustrated information about the interventions. Study team members will assist with demonstrating appropriate technique for applying interventions and will use the teach-back method to ensure comprehension and understanding. Interventions will be developmentally tailored to the infant's GA (Table 1) as follows:

1. Modified FNI portion of the bundle includes:

[figure not shown]
- a. Vocal soothing: mothers will be instructed to express their feelings to their infant in their native language using varying intonations
- b. Scent exchange: on initial visit, mothers will receive 2 cloths, 1 to place in her bra and 1 to place under her infant's head. Cloths are subsequently exchanged at each visit.
- c. Comforting touch: mothers will be instructed to use gentle but firm and sustained touch by placing the infant's arms on the chest and placing their hand on top. The other hand will be used to gently contain the infants' feet, lightly drawing the knees towards the chest.
- d. Mother-Kangaroo-Care plus: kangaroo care will be combined with gentle touch, vocal soothing and eye contact as described above.
- 2- Infant massage: mothers will be taught moderate pressure massage by PT
- 3- Parent-administered PT: 10 minutes interventions promoting postural and head control as well as midline orientation will be conducted by the mother is recommended starting at 33 weeks' PMA. The intervention will be monitored by a physical therapist for 3 consecutive sessions and weekly thereafter.

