Mothers/Fathers whose infants are randomized to the intervention group will be encouraged to be at the bedside and provide the GA appropriate interventions once per day, 5 days per week (5/7).

Table 1: Developmental-Guided NICU based rehabilitation program

	Postmentrual Age (completed weeks)				
Interventions	23-25	26-28	29-32	33-36	≥37
Vocal soothing					
Scent exchange					
Comforting touch					
Kangaroo care plus					
Infant massage					
Parent-administered PT				_	

Standard of care (control group) (n=30): Parents of infants randomized to standard care will continue to be encouraged to touch, hold, and talk to their infants. They are also encouraged to perform kangaroo care based on unit guidelines. All infants in standard care will have a routine physical therapy consult at 28 weeks gestation. The infants will continue to be followed 2-3 times per week for 10-30 minutes per session by PT until discharge from hospitalization. Social work actively engages with parents of infants admitted to the NICU which will include the intervention and standard of care group. Social work provides ongoing parental support and strives to alleviate barriers to visitation. At time of discharge standard care will resume for both groups, which includes a referral to early intervention and a NICU follow up appointment with developmental pediatrics at 3 months PMA. Below is the study schedule.

Self-report activity logs (separately uploaded documents) will be used to monitor the fidelity of the program. Both groups will fill out the log and document what aspects of the program were performed, the date, and duration of the intervention. Weekly interviews will be conducted with parental participants to evaluate the acceptability (satisfaction), feasibility (practicality) and fidelity (engagement) of the program. Weekly interviews will be done at the bedside with parental participants and a research team member to discuss any challenges or barrier to applying the recommended evidence based practice interventions. Examples of interview questions are 1) How are things going? 2) Do you have any questions about the interventions? 3) Are there things that are preventing you from doing the interventions? Additionally, research team members will perform random direct observations of intervention application to further evaluate feasibility and fidelity.

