#### Data management and statistical analysis

IRB approval and informed consent will be obtained prior to the start of the study. Video recorded GMA is standard of care in the NICU for neonates born ≤32 week's gestation and/or ≤1500 grams birthweight. Videos will be reviewed and scored independently by at least 2 of the study investigators. Videos will be scored with only the PMA information available to the investigator at the time of review. Inter-rater and intra-rater agreement will be assessed using Cohen's kappa (kappa) and percentage agreement. In case of

disagreement, the videos will be reviewed by all study members trained in the GMA and a consensus will be obtained.

The UVA NICU admits an average of 112 very low birth weight infants every year among which 83 are born at 32 weeks' gestation or less. We anticipate that, in one year of accrual, there will be approximately 120 infants <32 weeks gestation and/or ≤1500g birth weight. Based on a preliminary assessment of children in the NICU, we expect that 80% of these children will be eligible for the study. Recruitment acceptance rates of previous studies conducted in our NICU range from 30-50% for intervention studies and 80-90% for noninvasive studies. Using an acceptance rate of 80% yields an expected accrual of 70 patients per year. Allowing for 10% dropout, accrual of 33 patients per group (power calculation below) can be completed in 1 year.

Quantitative data will be analyzed using descriptive statistics and content analysis will be performed for qualitative responses. Quantitative data will be analyzed using the newest version of SPSS. Due to the exploratory purpose of the specific aim, descriptive statistics will be computed for all quantitative variables (demographic characteristics, recruitment, refusal, retention, follow up rates, % completion of self-report log and number of visitations per unit log). Frequencies and rates will be calculated for categorical variables and means and standard deviations will be calculated for continuous variables.

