Qualitative analysis will included semi-structured interviews with adult participants as well as direct observations using qualitative description. Qualitative descriptive analysis will provide a comprehensive evaluation of the NICU multimodal rehabilitation program. The textual data from the interviews and observation notes will be analyzed by (1) immersion in the data (2) followed by line by line analysis and data reduction of the textual data through inductive open coding and constant comparative analysis. Tentative categories will be listed with each line of data and identified by "nodes" in the Dedoose software. (3) After line-by-line analysis of the transcripts, categories ("nodes") will be grouped together to form tentative themes.

Repeated measures models will be used to compare HINE and TIMP total scores at the time of discharge and at 3 months PMA between newborns in the standard care group and in the intervention group (NEO rehab program). F-tests based on contrasts will be used to make comparisons at the two specific time points. To approximate the power of the F-test for comparing the groups with respect to the 3-month HINE scores, the results in Romeo et al.(2008) were used. Their study showed that across CP diagnoses, the average 3 –month HINE score was approximately 40 with an estimated standard deviation of 8.8. A score of below 40 is associated with the GMFCS IV and V levels while a score of 40-60 is associated GMFCS levels I and II at 3 months of age. A score ≥ 73 is optimal. With 30 subjects per group, the two-sample t-test has 80% power, with a 2-sided significance level of 5% when the effect of the intervention is to increase HINE scores by 6.5 points. Allowing for 10% dropout, 33 patients per group are required. Similar analyses will be used for the TIMP scores as well as subscales of the HINE. For the GMA assessments, we will tabulate the proportion of children in each group classified as having poor repertoire, cramped/synchronized or chaotic movement abnormalities at each of the followup times. Markov models will be used to assess how the intervention affects the proportions of children transitioning between classifications. For all of the endpoints; this study will provide estimates of variation useful for planning a larger study of the rehabilitation program. Our primary analysis will be done as intention-to-treat.

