### **Ethics**

HSR IRB approval (#21502) was obtained prior to initiating any study procedures.

This proposed research will in human subject research. Institutional Review Board will be obtained. Informed consent will be obtained (supplemental attachment).

This proposal seeks to investigate the acceptability, feasibility, fidelity of a neonatal intensive care unit (NICU) rehabilitation program that will consist of gestational appropriate interventions. Additionally, we will determine the effects of short term motor outcomes of the program in premature infants identified to be at risk for cerebral palsy (CP). Will seek to enroll 60 participants.

Recruitment and Retention Strategies: Our study team has existing relationships with the academic NICU. The PI is a member of the Neuro NICU team. Study participants will have the opportunity to learn about the research and ask questions and make suggestions. The study participants will be meeting with a member of the research team weekly. Recruitment and retention rates will be monitors and considered an outcome measure to determine acceptability of the program.

Recruitment and Informed Consent

Participants will be recruited after IRB approval at the University of Virginia has been obtained. Patients will be recruited from the NICU after meeting the outlined inclusion/exclusion criteria. Informed consent will be obtained for all participants. There will be opportunities to ask questions, and are informed that they may withdraw from any part of the study at any time. Randomization will not occur until consent is obtained.

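### Two enrolment targets conflict: 60 infants (30 per arm) in Aim 1, the arm descriptions and Ethics, but 33 per group (66) in the accrual and power text

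*Combined protocol and SAP*

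**What the plan says.** Four places in the combined protocol and SAP put enrolment at 60:

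- Study goals and objectives, Aim 1: "Enroll 60 preterm infants".
- The description of the intervention arm, under Inclusion and exclusion criteria, gives n=30.
- The description of the standard of care arm also gives n=30.
- Ethics: "Will seek to enroll 60 participants".

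Two places, both under Data management and statistical analysis, put it at 33 per group:

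- The accrual paragraph, after allowing for 10% dropout: "accrual of 33 patients per group (power calculation below) can be completed in 1 year".
- The power paragraph, which starts from "With 30 subjects per group, the two-sample t-test has 80% power" (two-sided 5%, an increase of 6.5 HINE points, SD 8.8) and concludes "Allowing for 10% dropout, 33 patients per group are required".

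The total of 66 is not printed; it is 2 × 33. The Project summary places HINE among the secondary outcomes: "Secondary short-term developmental outcomes will be measured using the Hammersmith Infant Neurological Examination (HINE) instruments". Problems anticipated/encountered names feasibility as the primary endpoint.

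**The concern.** In the power paragraph, 30 per group is the number to be analysed and 33 is the number to be enrolled so that about 30 remain. Aim 1, the arm descriptions and Ethics use 30 per group as the number enrolled. Both cannot be the enrolment target.

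Two things follow. It is unclear whether stopping at 60 would be completion or a shortfall of six. It is also unclear which power applies to the 3-month HINE comparison: the stated 80% holds under the plan's dropout assumption only if 33 per group are enrolled. This is the plan's only power statement, it supports the Aim 2 hypothesis about motor scores, and the results are meant to inform a larger trial. Readers of the HINE result, whichever way it falls, will need to know the planned size.

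**Working it through.** **Inputs**

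| Input | Value | Source |
|---|---|---|
| Difference in 3-month HINE | 6.5 points | power paragraph |
| SD | 8.8 | power paragraph |
| Test and level | two-sample t-test, two-sided 5% | power paragraph |
| Dropout | 10% | accrual and power paragraphs |
| Enrolment, first reading | 60 (30 per group) | Aim 1, arm descriptions, Ethics |
| Enrolment, second reading | 66 (33 per group) | accrual and power paragraphs |

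Equal allocation is taken from the arm sizes and the block sizes of 2 and 4.

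**Formula.** The standardised difference is d = 6.5 / 8.8 = 0.739. With n analysed per group, the noncentrality is λ = d × √(n/2) on 2n − 2 degrees of freedom. Power is the probability that a noncentral t with these parameters falls outside the two-sided 5% critical values.

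**Step 1: reproduce the plan.** For n = 30, λ = 0.739 × √15 = 2.86 on 58 degrees of freedom, and power is 80.3%. The stated 80% reproduces.

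**Step 2: reproduce the dropout allowance.** 30 × 1.10 = 33, as stated. (Dividing by the retained fraction gives 30 / 0.9 = 33.3, or 34 after rounding up. That is a separate, trivial point.)

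**Step 3: apply 10% dropout to each target.**

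| Enrolled | Analysed | Per group | Power for 6.5 points | Difference with 80% power |
|---|---|---|---|---|
| 60 | 60 × 0.9 = 54 | 27 | 75.9% | 6.84 |
| 66 | 66 × 0.9 = 59.4 | 29.7 | 79.9% | 6.51 |
| Plan's analysed number | 60 | 30 | 80.3% | 6.47 |

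**Step 4: size of the gap.** The targets differ by 66 − 60 = 6 infants, 3 per group, which is too many for rounding. Enrolling 60 rather than 66 costs 79.9 − 75.9 = 4.0 percentage points of power, or 6.84 − 6.51 = 0.33 HINE points on a 0–78 scale.

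**The case against.** The best case on the other side is that this is an editorial slip of little consequence. The number before dropout was probably carried into the enrolment statements. The loss is about 4 points of power on a secondary endpoint, no feasibility threshold in Table 2 depends on 60 versus 66, and the power figure is offered only as an approximation, using an SD from one outside study across CP diagnoses. An SD of 9.3 instead of 8.8 (an illustrative assumption, not a figure in the documents) would take power at 30 per group from 80.3% to 75.9%, the same loss as falling to 27 per group.

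All of that stands as a limit on materiality. It does not reconcile the two targets. Reading 60 as evaluable infants fails because Aim 1 and Ethics both speak of enrolling that number.

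Two cautions about moving up to 66 also stand:

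- The plan's expected accrual of 70 per year rests on 80% acceptance. The same paragraph reports 30–50% for earlier intervention studies in this unit. With its 120 infants and 80% eligibility, that gives 120 × 0.8 × 0.3 = 28.8 to 120 × 0.8 × 0.5 = 48 per year, short of either target in one year.
- Ethics reports IRB approval and a target of 60, and the documents do not show what number was approved.

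**Conclusion.** The concern holds. The current text gives two enrolment targets, six infants apart, and does not say which governs. If it is 66, the power statement is sound at about 80%. If it is 60, the stated 80% for 6.5 points does not follow from the plan's own dropout assumption: power is about 76%, and 80% power needs about 6.8 points.

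These figures use the plan's difference, SD and dropout rate, with equal losses in the two arms and a complete-case t-test. The planned repeated measures model may recover a little through the discharge scores, but the documents give no correlation, so the amount cannot be computed. The primary outcomes are unaffected. The inconsistency should be fixed because enrolment size is a basic design parameter, not because the power loss is large.

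**What to change.** State one enrolment target throughout.

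- **If 60 is intended:** keep Aim 1, the arm descriptions and Ethics. Restate the accrual and power paragraphs as 30 enrolled per group and about 27 evaluable, with about 76% power for 6.5 HINE points (80% for about 6.8).
- **If 33 per group is intended:** change Aim 1 and Ethics to 66 in total and the arm descriptions to n=33 each. Leave the power statement as it is.

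The first option costs wording only. The second is also wording in the protocol if 66 was always the working target; if 60 was, it means six more infants. Under the second option, check the number approved by the IRB, and do not rely on the projected 70 per year without allowing for a lower acceptance rate.

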# Quality assurance

Human Subject Research Institutional Review Board approved study DSMB not required for this project

### Expected outcomes of the study

Acceptability, feasibility and fidelity will be evaluated to ensure that the study design is sound for a future full-scale intervention study, Table 2.

- Acceptability using recruitment, refusal, retention, and follow up rates as well as weekly interviews with parental participants
- Feasibility (practicality) using direct observations and weekly interviews with parental participants
- Fidelity (adherence, exposure and engagement) using visitation data, activity logs, direct observations, and weekly interviews

Table 2: Primary outcomes

Variable	Concept	Domain	Metrics
Acceptability	Satisfaction	Correct, consistent and continuous use of the program	1. ≥75% Recruitment rates 2. <10 % Refusal rates 3. 75% Retention rates
			

4. 90% Follow-up rates

5. Weekly interviews with parental participants

Feasibility	Practicality	Adequacy of the logistics a) determining the capability of carrying out the program as planned b) identifying difficulties in applying any aspect of the program	Direct observations     Weekly interview the parental participants
Fidelity	Adherence	a) pro portion of the program content, b)methods and c) activities	1.>75% Completion of self-report activity log to be completed by parental participant 3.Direct observations by research team member
Fidelity	Exposure	a) number of sessions, b) attendance, c)frequency and d) duration	1. Self-report activity log to be completed by parental participant 3. Direct observations by research team member 4. Administrative data (NICU visitation log)
Fidelity	Engagement	Participation in the program	1. Weekly interviews conducted by research team member with parental participants 2. Administrative data (NICU visitation log) 3. >75% Completeness of the activity logs

The short-term impact of these combined interventions on motor function will be assessed using the HINE, theGMA and the TIMP. These instruments will be administered at time of discharge from the NICU and at 3 months PMA. These instruments used in combination are recommended to be administered to infants before 5 months PMA and provide the most predictive of risk for CP. Instruments will be administered by certified providers and/or therapists. Additionally, demographic characteristics of the sample will be collected using the medical record and include: gender, ethnicity, race, gestational age at birth, birth weight and head circumference, primary diagnosis, neurologic comorbidities, medication management of neurologic comorbidities and neonatal abstinence syndrome, NICU length of stay,

feeding method upon discharge, discharge head circumference, geographical region, and disposition (death or discharge home).

Table 3: Short term developmental outcomes

Instrument	Measurement	Age	Interval
HINE	26 items used to assess cranial nerve function, posture, quality and quantity of movements, muscle tone, and reflexes and reactions). Each item is scored individually 0-3 with a sum score of all individuals ranging from 0-78. Lower the score the poorer the motor function. The HINE allows for identification of early signs of CP and individual items have demonstrated predictive value of motor outcome. Sensitivity 90% for prediction of motor outcome.	2 and 24 months of age	At time of discharge and 3 months PMA
GMA	Writhing stage 1) normal 2) poor repertoire- monotonous and lack complexity 3) cramped-synchronized- appear rigid and are not smooth or fluent in character. 4) chaotic -characterized by abrupt, large amplitude movements involving all limbs. Fidgety stage 1) normal 2) abnormal fidgety movements-absent or abnormal (exaggerated). Cramped-synchronized followed by absent fidgety pattern, have a 98% sensitivity and specificity for prediction of CP	Writing movements birth-9 weeks Fidgety movements 9- 20 weeks	Every 2 weeks during hospitalization and 3 months PMA
TIMP	28 observed items of spontaneous movements and 31 elicited items that assess the child's motor responses scored 0-6. The lower the score the poorer the motor function. The test is sensitive to age-related changes in motor performance ( $r = 0$ .83).	32 weeks to 4 months post term	At time of discharge and 3 months PMA

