#### STUDY DESIGN

Methodology: The design will be a RCT at a single site academic NICU-UVA Hospital in Charlottesville Virginia. Randomization will be stratified by birth weight (< 1000 grams and 1000-1500 grams) using a randomly permuted block design with random block sizes of 2 and 4. The intervention group will receive a novel multisensory, multimodal rehabilitative program, which will incorporate elements from the FNI program (scent exchange, touch, vocal soothing) as well as infant massage and parent-administered physical therapy. The intervention will be adjusted to take into account the infant's developmental stage and physiologic stability (See **Table 1**). Additionally, the intervention focuses heavily on interventions the parent can provide.

[figure not shown]

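### The only visible numeric fidelity targets concern log completion, so the adherence target could be met while little of the program is delivered

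*Combined protocol and SAP*

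**What the plan says.** Table 2 splits fidelity into three rows.

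- **Adherence.** The domain is "a) pro portion of the program content, b)methods and c) activities". The metrics are "1.>75% Completion of self-report activity log to be completed by parental participant 3.Direct observations by research team member".
- **Exposure.** The domain is "a) number of sessions, b) attendance, c)frequency and d) duration". The metrics are data sources (activity log, direct observation, visitation log) with no numeric target.
- **Engagement.** The one number is "3. >75% Completeness of the activity logs".

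The intended amount is in the intervention description under Inclusion and exclusion criteria: parents are encouraged to "provide the GA appropriate interventions once per day, 5 days per week (5/7". The same section has both groups keep the log and "document what aspects of the program were performed, the date, and duration of the intervention". The Study design section adds: "The intervention will be adjusted to take into account the infant's developmental stage and physiologic stability".

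Data management and statistical analysis names the fidelity variables to be summarised as the percentage "completion of self-report log and number of visitations per unit log".

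**The concern.** The adherence domain asks how much of the program was carried out. The only number attached to it asks how much of a form was filled in. These can differ widely. Controls fill in the same log but have no schedule of five program sessions a week, so log completion cannot by itself mean program delivery.

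The exposure row is where sessions and their frequency belong. It has no visible target, and the analysis list reaches it only through visit counts. A visit is not a session, and neither sessions delivered nor their duration is listed. The schedule of five per week is never used as a denominator.

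Table 2 exists to show whether the design is sound for a full-scale trial. That trial needs the share of the program families actually deliver. The same figure is needed to interpret a null result on the motor outcomes: without it, an ineffective program cannot be told from one that was not given.

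**Working it through.** The documents derive no figure for the 75% targets, so there is none to reproduce. The check is what a result that meets the target allows for delivery.

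**Inputs from the plan.** Intended sessions: 5 per week. Log target: above 75%. Intervention arm: 30 infants. Dropout allowance: 10%.

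**Assumptions (the documents give none of these).** Recorded delivery r on logged days; share u of intended days on which the infant was not stable enough; between-infant SD of the delivery proportion; length of stay.

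**1. Full log, few sessions.** Log score 5/5 = 100%. Delivery 2/5 = 40%. This holds whether completion means a day with an entry or fields filled per form. Only if completion meant planned sessions done would the score be 40% and miss the target.

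**2. Incomplete log that still passes.** Over an assumed 8-week stay, intended sessions are 5 × 8 = 40. Entries on 31 days give 31/40 = 77.5%, which passes. If 8 sessions were given, delivery is 8/40 = 20%.

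**3. Unlogged days.** Let c be the share of intended days logged. True delivery lies between c × r (no session on any unlogged day) and c × r + (1 − c) (a session on every one).

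| c | r | Lower | Upper |
|---|---|---|---|
| 0.76 | 0.40 | 0.76 × 0.40 = 30% | 0.304 + 0.24 = 54% |
| 0.76 | 0.80 | 0.76 × 0.80 = 61% | 0.608 + 0.24 = 85% |
| 1.00 | 0.40 | 40% | 40% |

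The width is 1 − c = 24 points when the target is only just met. Excluding unlogged days instead returns r itself.

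**4. Days when the infant was not stable enough.** If these leave the denominator and all sessions fell on other days, 2 of 5 becomes 0.40/(1 − u): 44%, 50% and 57% for u = 0.10, 0.20 and 0.30.

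**5. Precision of mean delivered/intended.** The 95% half-width is t × SD/√n.

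| n | SD 0.20 | SD 0.30 |
|---|---|---|
| 30 | ±7.5 points | ±11.2 points |
| 27 (30 × 0.90) | ±7.9 points | ±11.9 points |

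Thirty infants are therefore enough to separate 40% delivery from 75% under these SDs.

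**The case against.** The strongest reply is that the plan already separates the constructs and collects the data. Sessions and frequency belong to exposure, so a family giving few but complete sessions has low exposure and not necessarily low adherence. That stands, and the fix keeps the two apart. Logs record what was done, when and for how long; visits are counted; direct observation and weekly interviews add to this. That also stands: what is missing is a stated measure and its definition, not data.

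The plan attaches no go/no-go decision to the 75% figure, so meeting it triggers nothing by itself. The log form is a separate upload and might define completion. The adherence and exposure cells skip item 2, so a metric may not have survived in the text available. Parents are encouraged, not required, to reach five a week, so using that as a denominator is an interpretation. These limit the point. They do not remove it, because the statistical section, in running text, still names only log completion and visits for fidelity.

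Two stronger readings are tempting and not supported:

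- A reader might infer that the plan ignores sessions or leaves exposure out of the analysis. It does not: exposure is a primary-outcome row, and visits are among the listed variables.
- A reader might infer that the recruitment (≥75%) and refusal (<10%) limits contradict each other. They would conflict only if refusal meant every non-acceptor. If only active declines count, or if acceptance exceeds 90%, both can be met. Refusal, recruitment, retention and follow-up rates all lack stated denominators. That is a wording clarification, separate from this point.

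**Conclusion.** The point holds on the visible text. The adherence target, read as the statistical section words it, measures record keeping and could be met with little of the program delivered: 100% on the target against 40% on delivery in the simplest case. That comparison needs only the plan's schedule and a parent who gives 2 of 5 sessions. The 24-point spread from unlogged days assumes that completeness means the share of intended days logged. The figures for unstable days and precision are illustrations under assumed values. Confidence is medium because the log form and possibly one table item are out of view. It should be fixed: a primary outcome may be misread, and the repair is cheap. If the sponsor meant completion as planned sessions carried out, one sentence saying so would resolve the adherence wording; the exposure measure would still need stating.

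**What to change.** In the intervention arm, from data the log already records:

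1. **Adherence.** Report the share of Table 1 components applicable at the infant's postmenstrual age that were performed in delivered sessions.
2. **Exposure.** Report sessions delivered divided by sessions intended, using the plan's own five per week from randomisation to discharge. Report separately the days when the infant was not stable enough. Give the figure with unlogged days counted as not delivered and again with them excluded, each with a 95% confidence interval. Cross-check against the visitation log.
3. Add both to the quantitative variables in Data management and statistical analysis, define completion, and keep log completeness as a data-quality measure.

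Whether the 75% target moves to either measure is the sponsor's choice.

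Cost: Table 2 wording, one line in the statistical section, two derived variables, and a note of days when the infant was not stable enough. No extra visits or infants are needed. The downside is a probably less flattering figure and some work matching logs to the visitation log.
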